9.2.3. Version 4.0: 28 November 2023

Overall reason for Version 4.0: The main reasons for Version 4.0 were to clarify study procedures in cases of DTIC interruption and revise the analysis of the key secondary endpoint (OS). Additional updates were made to reflect changes in study staff, improved clarity, and to address clerical errors. A summary of changes from global Version 3.0 to Version 4.0 is presented below.

Item No.	Protocol Section	Summary of Change	Reason/ Rationale
1	Title Page	ClinicalTrials.gov study number was revised.	The ClinicalTrials.gov identifier number was corrected.
2	Signature Page	Titles of PTC signatories were updated.	Change in signatory titles.
3	Protocol Identifiers and Study Personnel	Study personnel was updated	Change in PTC study staff.
4	Synopsis, Section 8.2, Section 8.4.3	It was clarified that a hierarchical testing procedure will be utilized.	Revisions were made to address the FDA comments and to
		The power calculation and analyses of OS were revised to specify that the interim analysis will occur when at least 60% of the events have accumulated and the final analysis will occur when 184 events have accumulated.	provide more flexibility in the timing of the interim OS analysis, which is planned to be done at the time of the final efficacy analysis for PFS.
5	Synopsis, Section 4.1	Inclusion criterion #11 revised as follows: Old version: "AST or ALT <3 times the ULN" New version: "AST and ALT <3 times the ULN."	Correction of clerical error
6	Synopsis, and Section 5.1	The 200 mg/vial DTIC strength was removed, along with volume of Sterile Water for reconstitution. New text : DTIC for injection will be provided (by the site or by the sponsor) and will be reconstituted with Sterile Water for Injection, USP.	Text revised to allow for site- and country- specific variations in specific strengths of DTIC.
7	Synopsis, Footnote "a" in Schedule of Assessments, Figure 1 footnote, Section 3.1, Section 7.1	New text added (indicated in bold): Survival follow-up will continue every 3 months until the later of 184 events or 2 years after the last subject is randomized	Revision made to ensure that sufficient events are achieved for analysis of OS.
8	Schedule of assessments, Footnote b	"Window" was substituted with "span" to clarify that procedures performed on Cycle 1 Day 1 and Cycle 2 Day 1 can be done over a 48-hour period.	Clarification

 Table 13:
 Summary of Changes From Global Protocol Version 3.0 to 4.0

Item No.	Protocol Section	Summary of Change	Reason/ Rationale
9	Schedule of assessments, Footnote g	For subjects who have DTIC interrupted or held, it was added that clinical laboratory assessments will be required weekly for the first 3 weeks after DTIC reintroduction. For subsequent cycles, the clinical laboratory assessments may be performed at a minimum of once per cycle or more frequently per the investigator's discretion to ensure that the subject meets the protocol- defined safety criteria.	Improved safety monitoring for subjects who require interruptions in DTIC
10	Schedule of assessments, Footnote q	In footnote q, the bolded text was added: If DTIC is interrupted in Cycle 3 then PK sampling should be performed upon reintroduction of DTIC as described in footnote "n"	Clarification
11	Section 3.3	The following statement was added: DTIC should be reintroduced at least 48 hours after unesbulin dosing	Additional instructions for clarity
12	Section 4.3	The following statement was added: Subjects who fail screening may be considered for rescreening after consultation with the PTC Medical Monitor.	Procedural change
13	Section 5.6	Bolded text added: The investigator and study staff (including processing laboratory personnel), the subjects, and the sponsor's staff (with exception of Pharmacovigilance staff for the purposes of SUSAR reporting) will remain blinded until the primary analysis is completed.	Clarified that study will remain blinded until the primary analysis is completed rather than study closure, which could be later than the primary analysis. It was also clarified that certain Pharmacovigilance staff at PTC will unblind some subjects for SUSAR reporting purposes.
14	Section 8.1	Null and alternative hypotheses for the key secondary endpoint were added.	Clarification

Abbreviations: ALT, alanine aminotransferase; AST, aspartate aminotransferase; DTIC, dacarbazine; OS, overall survival; PFS, progression-free survival; PK, pharmacokinetic; SUSAR, suspected unexpected serious adverse reaction; ULN, upper limit of normal

10. **REFERENCES**

1. INTRODUCTION AND OVERVIEW

The purpose of this statistical analysis plan (SAP) is to describe the procedures and statistical methodology to be implemented for data analysis of the study described in protocol PTC596-ONC-008-LMS (Global Version 4.0; 28 November 2023). It also covers any later amendments to the protocol that may be produced that have no material effect on the statistical analysis (refer to relevant file note(s), if applicable). However, if circumstances arise during the study such that more appropriate analysis procedures or methodologies become available/are warranted, or if there is a protocol amendment which necessitates changes to the SAP, then this document will be revised. Any deviations from the SAP will be substantiated by sound rationale and will be documented in the clinical study report (CSR). Otherwise, the CSR will consider all the information defined in this SAP.

Table, figure, and listing specifications are contained in a separate document.

1.1. Study Design

This is an international, multicenter, randomized, double-blind, placebo-controlled, Phase 2/3 study to compare the efficacy and safety of unesbulin plus dacarbazine (DTIC) versus placebo plus DTIC in subjects with unresectable or metastatic, relapsed or refractory leiomyosarcoma (LMS) who have received at least 1 prior line of systemic therapy.

Eligible subjects will be randomized 2:1 (unesbulin plus DTIC: placebo plus DTIC) to one of the following treatment groups as shown in Figure 1:

- Unesbulin plus DTIC: Unesbulin 300 mg will be administered PO twice weekly (BIW) in each 3-week treatment cycle. DTIC 1000 mg/m² will be administered IV once every 21 days (Q21D).
- **Placebo plus DTIC**: Matching placebo will be administered PO BIW in each 3-week treatment cycle. DTIC 1000 mg/m² will be administered IV Q21D.

Figure 1: Study Design

Abbreviations: AE, adverse event; BIW, twice weekly; DTIC, dacarbazine; EOT, end-of-treatment; FUP, follow-up; OS, overall survival; Q21D, once every 21 days

Note: All subjects will receive treatment until evidence of disease progression, unacceptable toxicity, or other withdrawal criteria are met. An EOT assessment will be performed within 30 days after the end of treatment or until recovery or stabilization of the AE, whichever occurs latest. For subjects requiring immediate initiation of a new treatment option, an EOT visit may be completed earlier. A safety FUP assessment should be performed by phone at

30 days (±3 days) after the EOT. Survival FUP assessments will occur by phone every 3 months (±7 days) after the EOT visit until the later of 184 events or 2 years after the last subject is randomized.

For approximately 300 subjects with 1 to 3 prior lines of treatment, randomization will be stratified as follows:

- Number of prior systemic therapies (1 or >1)
- Eastern Cooperative Oncology Group (ECOG) performance status (PS) score (0 or 1)
- Histological tumor type (uterine versus nonuterine LMS)

Forty-five subjects with at least 4 prior lines of treatment will be randomized and stratified as follows:

- ECOG PS score (0 or 1)
- Histological tumor type (uterine versus nonuterine LMS)

1.2. Study Objectives and Endpoints

Table 1:Study Objectives and Endpoints

Objectives	Endpoints
Primary Objective: PFS of unesbulin plus DTIC versus placebo plus DTIC	Primary Endpoint: PFS per RECIST 1.1 assessed by an independent central imaging laboratory.
Key Secondary Objective: Efficacy : OS of subjects treated with unesbulin plus DTIC versus placebo plus DTIC	Key Secondary Endpoint: Efficacy: OS
Other Secondary Objectives: Efficacy : Antitumor activity of unesbulin plus DTIC versus placebo plus DTIC	 Other Secondary Endpoints: Efficacy: ORR (proportion of subjects with BOR of either CR or PR) DCR or CBR, defined as the proportion of subjects with BOR of CR, PR, or at least 3 months of SD DoR
Safety : Safety and tolerability of unesbulin plus DTIC versus placebo plus DTIC	Safety : Vital signs, physical examination, ECG, laboratory abnormalities, ECOG PS scores, and AEs
Exploratory Objectives: Efficacy : Evaluate the antitumor activity of unesbulin plus DTIC versus placebo plus DTIC in subjects with at least 4 prior lines of treatment.	Exploratory Endpoints : Efficacy : PFS, OS, ORR, DCR, and DoR in subjects with at least 4 prior lines of treatment.
 PK: Evaluate the PK of unesbulin in the presence of DTIC in subjects with LMS Evaluate the PK of DTIC/AIC alone and in the presence of unesbulin in subjects with LMS. 	 PK parameters of unesbulin in subjects who receive unesbulin plus DTIC: C_{max}, T_{max}, and AUC_{0-t} PK parameters of DTIC and its inactive metabolite AIC in subjects who receive

Objectives	Endpoints
	unesbulin plus DTIC and placebo plus DTIC: Cmax, Tmax, and AUC _{0-t} .
PROs : Compare the effect of unesbulin plus DTIC versus placebo plus DTIC on PROs, including HRQoL assessments.	PROs: 30-item score EORTC QLQ-C30 and EQ-5D-5L
Biomarkers : Measure genotype of subject tumors, assessed by blood sampling, at baseline and posttreatment	Biomarkers : Genetic evaluation of the tumors by analyzing ccfDNA

Abbreviations: AE, adverse event; AIC, 5-amino-imidazole-4-carboxamide; AUC_{0-t}, area under the concentration versus time curve from time zero to the last sampled time or the last non-zero concentration; BOR, best overall response; ccfDNA, circulating cell-free tumor DNA; CBR, clinical benefit rate; CR, complete response; DCR, disease control rate; DoR, duration of response; DTIC, dacarbazine; ECG, electrocardiogram; ECOG, Eastern Cooperative Oncology Group; EORTC QLQ-C30, European Organisation for the Research and Treatment of Cancer Quality-of-Life Questionnaire; EQ-5D-5L, EuroQol 5-level EQ-5D version; HRQoL, health-related quality-of-life; ORR, objective response rate; LMS, leiomyosarcoma; OS, overall survival; PFS, progression-free survival; PK, pharmacokinetic; PR, partial response; PROs, patient-reported outcomes; PS, performance status; RECIST, Response Evaluation Criteria in Solid Tumors; SD, stable disease

1.3. Sample Size

The target sample size is approximately 345 (300 subjects with 1 to 3 prior lines of systemic therapy for the primary analysis and 45 subjects with at least 4 prior lines of systemic therapy for the exploratory analysis).

The sample size was computed based on the comparison of progression-free survival (PFS) between subjects randomized to unesbulin plus DTIC and subjects randomized to placebo plus DTIC. Full details of the sample size assumptions are provided in the study protocol.

1.4. Randomization

Subjects will be randomized 2:1 to either unesbulin plus DTIC or placebo plus DTIC using a central randomization system. For subjects with 1 to 3 prior lines of treatment, randomization will be stratified by the number of prior systemic therapies (1 or >1), ECOG PS score (0 or 1), and histological tumor type (uterine or nonuterine LMS). For subjects with at least 4 prior lines of treatment, randomization will be stratified by ECOG PS score (0 or 1) and histological tumor type (uterine or nonuterine LMS).

1.5. Assessment of Efficacy

Response assessments will be performed by radiological imaging using Response Evaluation Criteria in Solid Tumors (RECIST) 1.1 criteria every 6 weeks (\pm 7 days) until disease progression. After Cycle 8, scans are to be performed every 9 weeks. If any subject responds with a complete response (CR) or partial response (PR) at any assessment, then the subsequent confirmatory scan should be performed 4 weeks after the previous scan where the objective response was first evidenced. Assessment of response and the primary endpoint, PFS, will be assessed by an independent central review (ICR) who will be blinded to treatment assignment.

Subjects should be followed with the same imaging procedure throughout the study. Computed tomography scans or magnetic resonance imaging may be used as clinically indicated. If the

subject withdraws for reasons other than tumor progression, an EOT scan should be performed if the last scan was \geq 3 weeks earlier.

2. ANALYSIS SETS

2.1. Intent-to-Treat (ITT) Set

The ITT set will include all randomized subjects. Subjects will be grouped based on the group they are randomized to. If a subject receives treatment in the group different from the one to which he/she was randomized, the subject's efficacy data will be analyzed "as randomized." The ITT population will be used as sensitivity analysis for all efficacy analysis.

2.2. Modified Intent-to-treat (mITT) Set

The mITT set will include randomized subjects with 1 to 3 prior lines of therapy. The mITT population will be used in all the efficacy analysis, including analyses of the primary and secondary endpoints. Subjects will be grouped based on the group they are randomized to. If a subject receives treatment in the group different from the one to which he/she was randomized, the subject's efficacy data will be analyzed "as randomized." The mITT Analysis Set is the primary analysis population for this study.

2.3. Safety Analysis Set

The safety analysis set will include all subjects who received at least one dose of study drug (unesbulin/placebo or DTIC). If a subject receives treatment in the group different from the one to which he/she was randomized, the subject's safety data will be analyzed "as treated." The safety analysis set will be used in the statistical analyses for safety.

2.4. Pharmacokinetic Analysis (PK) Set

The PK analysis set will include subjects in the safety analysis set who have at least one measurable plasma concentration of unesbulin, DTIC, or AIC.

3. GENERAL CONSIDERATIONS

3.1. General Considerations

Continuous data will be summarized using number of observations (n), arithmetic mean (mean), standard deviation, median, minimum value (min) and maximum value (max) by treatment group. Categorical variables will be summarized using the frequency count (n) and percentage (%) by treatment group. An overall/total group (i.e., sum of all treatment groups) will generally be presented additionally for summaries of disposition, demography, and baseline characteristics.

For all percentage calculations, the denominator will be the number of subjects in the analysis set for the treatment group, unless otherwise stated.

Only data from protocol scheduled visits will be included in the summary tables. Data from unscheduled visits will not be included in the summary tables but will be included in the by-subject listings. Descriptive summaries by visit and treatment will be provided for all the primary and secondary efficacy endpoints.

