5.3.1.1. Best Overall Response

BOR is defined as the best response designation recorded between randomization date and the date of objectively documented progression per RECIST 1.1 or the date of initiation of subsequent therapy or palliative local therapy, whichever occurs first. For subjects without documented progression or subsequent therapy or palliative local therapy, all available response designations will contribute to the BOR determination. For this study responses of CR or PR require confirmation by a subsequent assessment that is performed a minimum of 4 weeks or later from when the initial response is observed. Table 4 illustrates how CR or PR responses will be confirmed.

BOR will be summarized using counts and percentages by treatment group, this analysis will be based on subjects with measurable diseases with at least 1 post-randomization assessment.

First Time Point Response ^a	Second Time Point Response	Confirmed Response (Best Response) ^b
PD	No further evaluation	PD
NE	PD	PD
CR	PD	SD or PD ^c
PR	PD	SD or PD ^c
SD	PD	SD or PD ^c
CR	CR	CR
CR	NE ^a	SD or NE ^d
PR	CR	PR
PR	PR	PR

 Table 4:
 Confirmed Response Based on Subsequent Assessment

First Time Point Response ^a	Second Time Point Response	Confirmed Response (Best Response) ^b
PR	SD ^{ae}	SD
PR	NEª	SD or NE ^d
SD	CR	SD
SD	PR	SD
SD	SD	SD
SD	NE	SD or NE ^d
NE	CR	SD
NE	PR	SD
NE	SD	SD
NE	NE	NE

Abbreviations: CR, complete response; NE, not evaluable; PD, disease progression; PR, partial response; SD, stable disease.

^a Subsequent documentation of CR may provide confirmation of a previously identified CR for subjects where the second integrated response was NE. Subsequent documentation of PR may provide confirmation of a previously identified PR for subjects where the second integrated response was NE or SD. If the third TPR confirms the CR (or PR) then the Confirmed Response will be CR (or PR). For this study, only one (1) intervening NE is allowed between CRs/PRs. For example: CR NE CR = CR; PR NE PR = PR. Additionally, one (1) SD is allowed between PRs (e.g., PR SD PR = PR).

^b A Best Response of SD can only be made after the subject is on-study for a minimum of 35 days. If the subject is on study less than 35 days, any tumor assessment indicating stable disease before this time period will have a Best Response of NE unless PD is identified.

^c Best response will be SD if the first TPR is after 35 days on study. Otherwise, the best response will be PD.

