6.3. Physical Examination and Vital Signs

Physical examination will be summarized by nominal visit, and abnormal findings will be listed.

Vital signs (including systolic and diastolic blood pressure, respiratory rate, temperature, heart rate, weight, height, and BSA) will be summarized and presented as actual value and change from baseline at each scheduled nominal visit by treatment group. The number of non-missing values, mean, standard deviation, median, and range (minimum and maximum) will be presented. Change from baseline will be calculated as the postbaseline measurement minus the baseline measurement. If either the baseline or postbaseline value is missing, the observation will not be included in the change from baseline summary. The body temperature will be collected in °F or °C, but reported in °C. Weight will be collected in pounds (lb) or kilograms (kg) but reported in kg.

A listing of all vital sign assessments will be presented for the safety analysis set.

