6.5. Electrocardiogram (ECG)

ECG parameters (PR, RR, QRS, QT, QTcF, QTcB) and heart rate (HR) actual value and change from baseline will be summarized by treatment group and the overall population. Each subject's triplicate measurements will be averaged at a given time point before the summary. The number of non-missing values, mean, standard deviation, median, and range (minimum and maximum) will be presented. Change will be calculated as the post baseline measurement minus the baseline measurement. If either the baseline or postbaseline value is missing, the observation will not be included in the change from baseline summary.

In addition, a categorical analysis of QTc intervals will be performed for each time point.

The number and percentage of subjects in each QTc interval (<450 msec, 450-480 msec, 481-500 msec, >500 msec) will be summarized at baseline and each of the subsequent time points.

Categories of changes from baseline (\geq 30 msec and \geq 60 msec), maximum QTc intervals at all post dose time points, and maximum changes from baseline will be summarized by visit.

ECG results (PR, RR, QRS, QT, QTcF, QTcB, and classification of Normality, Abnormality with Clinical Significance, or Abnormality without Clinical Significance) will be presented in data listings.

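### The default percentage denominator in SAP 3.1 keeps unmeasured subjects in the by-time-point QTc percentages and understates them, most of all at ECG times taken only in the PK substudy

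*SAP*

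**What the plan says.** SAP 3.1 gives two general rules. On format: "Categorical variables will be summarized using the frequency count (n) and percentage (%) by treatment group". On the base: "For all percentage calculations, the denominator will be the number of subjects in the analysis set for the treatment group, unless otherwise stated". The second is a default that another section may override.

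Safety tables use the safety analysis set (SAP 2.3 and 6), which is everyone with at least one dose of either drug. Its size per arm is the same at every visit.

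The sections that produce by-visit safety tables are:

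- **SAP 6.5, absolute QTc bands.** The number and percentage of subjects in each of four bands, the top one above 500 msec, "will be summarized at baseline and each of the subsequent time points". No denominator is named.
- **SAP 6.5, change from baseline.** "If either the baseline or postbaseline value is missing, the observation will not be included in the change from baseline summary". Categories of at least 30 and at least 60 msec are then summarized by visit. Again no percentage denominator is named.
- **SAP 6.3, physical examination.** "Physical examination will be summarized by nominal visit, and abnormal findings will be listed". Neither a percentage nor a denominator is mentioned; the n-and-% format would come from SAP 3.1.

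Where the SAP wants a different base it can say so. For best overall response in SAP 5.3.1.1, "this analysis will be based on subjects with measurable diseases with at least 1 post-randomization assessment".

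**The concern.** A full-set denominator suits summaries of whether something ever happened on treatment, such as TEAEs, because every dosed subject is at risk of being counted. It does not suit a table of what was found at one time point, because a subject with no ECG then is counted as if the ECG had been done and fell outside every band. The bands no longer add to 100%, and each percentage is too low by the share of subjects not measured.

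ECG is a named safety endpoint (protocol 2.5, SAP Table 1), and a QTc above 500 msec is the kind of finding a reader looks for in this table. Outside the PK substudy, the on-treatment ECGs on Day 1 of Cycles 1 to 3 are taken about 2 hours after DTIC. Unesbulin is not given on the DTIC day. The Day 2 ECGs in the PK substudy are the only scheduled ones timed to an unesbulin dose, and these are the time points at which the default rule dilutes the percentages most.

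**Working it through.** The plan states no figure on this point, so there is none to reproduce. If *m* of the *N* subjects in an arm's analysis set are measured at a time point, and a proportion *q* of those measured have the finding, the default rule prints *q* × *m*/*N*. The correct by-time-point figure is *q*.

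**PK-only ECG time points (no attrition assumption)**

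Inputs:
- About 345 subjects (SAP 1.3), randomized 2:1 (SAP 1.4), with about 12 in the PK substudy (protocol 3.1).
- ECG times (footnotes i and j to the schedule of assessments): PK subjects have serial ECGs on Days 1 and 2 of Cycles 1 and 3. Other subjects have one ECG on Day 1 of Cycles 1 to 3.
- Assumptions: all randomized subjects are dosed, and the substudy also splits 2:1.

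Arms: 345 × 2/3 = 230 unesbulin and 345 × 1/3 = 115 placebo. Substudy: 12 × 2/3 = 8 and 12 × 1/3 = 4.

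- One unesbulin subject above 500 msec, among those measured: 1/8 = 12.5%.
- The same subject under SAP 3.1: 1/230 = 0.43%.
- Ceiling for all four bands together: 8/230 = 3.5% on unesbulin, 4/115 = 3.5% on placebo, 12/345 = 3.5% overall.

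**Visits that all subjects should attend**

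Treatment continues until progression, toxicity or withdrawal (protocol 3.1), so *m*/*N* falls over time. The documents give no time-on-treatment figures. As a rough proxy, take the planned PFS medians in protocol 8.2 (1.5 to 2.5 months on placebo; more than 4 on unesbulin, set here at 4) with exponential decline: share remaining = 0.5^(t/median).

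Cycle 3 Day 1 is week 6, so t = 42/30.4375 = 1.38 months.

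- Placebo: 0.5^(1.38/1.5) = 0.529 to 0.5^(1.38/2.5) = 0.682.
- Unesbulin: 0.5^(1.38/4) = 0.787.
- A finding present in 10% of those measured in both arms prints as 5.3–6.8% on placebo and 7.9% on unesbulin. The spurious ratio is 0.787/0.682 = 1.15 to 0.787/0.529 = 1.49.
- With medians of 2 and 3 months: 0.727/0.620 = 1.17.
- With equal medians the ratio is 1.00. Both arms are still understated, for example 6.2% instead of 10% with medians of 2 months.

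Physical examination continues on Day 1 of every cycle. On the same proxy, at Cycle 9 Day 1 (week 24) the shares are 8–22% and 38%, so a true 10% would print as 0.8–2.2% and 3.8%.

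With subjects measured at the visit as the base, 10% prints as 10% in both arms throughout.

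**The case against.** The strongest reply is that the consequence is small and the size uncertain. Its parts carry different weight.

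- **Change categories.** SAP 6.5 already leaves missing values out of the change-from-baseline summary, which plausibly covers the 30 and 60 msec categories. This stands in part: the sentence names no percentage denominator. It does not reach the absolute bands.
- **Timing of losses.** The first scheduled on-treatment scan is at about week 6, so imaging can remove few subjects before Cycle 3 Day 1. Smooth exponential loss from randomization probably overstates attrition there. This stands.
- **Arm difference.** A reader might infer that the rule will produce a false QTc difference between arms, for instance 6.2% against 7.9% (ratio 1.27) on medians of 2 and 4 months. The documents do not support stating that as fact. It rests on planned PFS medians as a proxy for time on treatment, and SAP 3.5 records that the monitoring committee recommended stopping for futility. The actual gap may be small or absent.
- **Late QTc signal.** A reader might also infer that late QTc findings are diluted. Scheduled on-treatment ECGs end at Cycle 3, so there is no long series of late ECG visits to dilute.
- **Physical examination.** SAP 6.3 does not mention percentages, and examinations between screening and end of treatment may be symptom-directed. The point applies there only if n and % are tabulated.
- **Other safeguards.** Counts accompany percentages, ECG results are listed by subject, maximum QTc is also summarized, and the separate table shells (SAP 8), which were not available, may name another base. These reduce the harm but do not change the rule as written.

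None of this touches the PK-only time points, where the dilution follows from the sampling schedule itself.

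**Conclusion.** The point holds as a default-rule problem in descriptive safety tables. It does not affect every percentage in the SAP, because the rule allows exceptions and best overall response uses one. No primary, key secondary or TEAE result changes.

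The firm part is the absolute QTc bands at PK-only ECG times: a true 12.5% of those measured prints as about 0.4%, and the bands together cannot exceed about 3.5%. This rests on planned numbers, on all subjects being dosed and on a 2:1 split in the substudy. If fewer than 345 subjects were dosed before the trial stopped, the overall ceiling becomes 12/N and rises accordingly.

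The softer part is shrinkage at the Cycle 2 and 3 Day 1 ECGs and at later physical examinations. Understatement there is certain once subjects leave treatment, but its size is not known. A distortion between arms is conditional: a ratio of 1.0 with equal attrition, up to about 1.15–1.49 at Cycle 3 on the planned medians, and probably less for the two reasons of timing and futility given above.

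**What to change.** Add to SAP 3.1, or to SAP 6.3 and 6.5: *For by-visit or by-time-point categorical summaries the denominator is the number of subjects with a non-missing assessment at that visit or time point (and a non-missing baseline for change categories); this n is shown per arm.*

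Keep the full-set denominator for ever-on-treatment summaries such as TEAEs and disposition.

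The cost is one SAP sentence and matching footnotes in the table shells. No data collection, efficacy analysis or error-rate control is affected. If the shells already use the measured subjects as the base, the sentence simply brings the SAP into line with them.
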